4.2. Participant Dispositions

Reasons for discontinuation prior to randomization including screen failure will be summarized for all participants who sign the informed consent form.

The number and percentage of participants who have completed or discontinued from the study or treatment will be summarized by treatment using the Randomized Population. The individual reasons for discontinuation will also be included in the summary. Comparison between LY3209590 and Insulin Degludec will be conducted using the Fisher's exact test.

A listing of the reasons for study/treatment discontinuations will be generated for the Randomized Population. A listing of the randomized treatment for this study will also be provided.

Time to permanent discontinuation of study treatment, time to study discontinuation and time to early discontinuation of study treatment due to AEs (if there is a sufficient number to warrant a summary) will be presented as a figure.

4.3. Primary Endpoint Analysis

4.3.1. Definition of Endpoint

The primary endpoint of this study is the HbA1c change from baseline to Week 26 (Visit 22). The HbA1c is reported in unit of % by central laboratory and will be converted to the unit of mmol/mol using the following formula: HbA1c in mmol/mol = 10.93 * HbA1c in % - 23.5 (http://www.ngsp.org/ifccngsp.asp). The HbA1c analysis will be conducted for both units.

4.3.2. Main Analytical Approach

The primary objective is to test the hypothesis that LY3209590 is noninferior to insulin degludec on glycemic control in the targeted study population. The noninferiority test will be based on: *treatment regimen estimand* for the US FDA submission and *efficacy estimand* for registrations in other countries. The full significance level of 0.05 will be used for each estimand.

	Treatment Regimen Estimand	Efficacy Estimand
Analysis	All participants in EAS1 with non-missing	All participants in EAS2 with non-missing
Population	baseline measure	baseline measure and at least one non-missing
		post-baseline scheduled measure
Analysis	All non-missing observations at baseline and	All non-missing observations at baseline and all
Data	Week 26 (Visit 22) regardless of the use of	scheduled post-baseline timepoints during
	study intervention or rescue medications.	treatment period (that is, Weeks 2, 4, 12, 16, 26,
		36, 52, 64 and 78) prior to the date of last study
		dose + 10 days for LY3209590 and +1 day for
		Insulin Degludec, or the initiation of rescue
		medication whichever is earlier (for participants
		with an intercurrent event).
Missing	There may be missing values at Week 26	There may be missing values due to the early
Data	(Visit 22) due to early study discontinuation.	discontinuation of study intervention or use of
	The missing values will be imputed using	rescue medication. The MMRM model will be
	multiple imputation by the retrieved dropout	used, and the missing values will be handled in
	approach. The retrieved dropout participants	the MMRM analysis under the assumption of
	are those who discontinue study intervention	missing at random.
	prior to Week 26 but have non-missing	
	measures at Week 26 in the same treatment	
	arm. If there are only a limited number of	
	retrieved participants (i.e., at least 1 arm has	
	less than 8 participants who discontinued	
	study treatment early and who have	
	endpoint visit measurements) or the model	
	cannot converge, the missing HbA1c at	

This table provides the details of treatment regimen estimand and efficacy estimand.

	Treatment Regimen Estimand	Efficacy Estimand
	Week 26 will be imputed by return-to-	
	baseline multiple imputation approach (Qu	
	and Dai 2022).	
Analysis	After the imputation, the observed and	The MMRM model will include treatment, strata
Model	imputed data will be analyzed by the	(country, and the type of basal insulin at
	ANCOVA model using treatment, strata	randomization), visit and treatment-by-visit
	(country, and the type of basal insulin at	interaction as fixed effects, and baseline of the
	randomization), and baseline value of the	dependent variable as a covariate. The Kenward-
	dependent variable as independent variables.	Roger approximation will be used to estimate
	The statistical inference will be based on the	denominator degrees of freedom for the MMRM
	multiple imputation framework by Rubin	models. An unstructured covariance structure will
	(1987).	be used to model the within-participant errors. If
		this structure fails to converge, the following
		covariance structures will be used in order until
		one converges:
		1. Toeplitz with heterogeneity
		2. autoregressive with heterogeneity 3.
		compound symmetry with heterogeneous
		variances
		4. Toeplitz
		5. Autoregressive
		6. compound symmetry without heterogeneous
		variances.

Abbreviation: ANCOVA = analysis of covariance; EAS1 = Efficacy Analysis Set 1; EAS2 = Efficacy Analysis Set 2; HbA1c = hemoglobin A1c; MMRM = mixed model repeated measurement.

The 2-sided 95% CI of the LS mean difference (LY3209590 – insulin degludec) in the HbA1c change from baseline to Week 26 (Visit 22) will be estimated. For both estimands, LY3209590 will be declared noninferior to insulin degludec if the upper limit of the 2-side 95% CI for the LS mean difference in the HbA1c (measured in %) change from baseline is below NIM of +0.4%. In addition, the 95% CI for the LS mean difference will be compared to an alternative NIM of +0.3%.

4.3.3. Sensitivity Analysis

Two-way Tipping Point Analysis

To confirm the robustness of the primary endpoint results in treatment regimen estimand, a 2way tipping point analysis represents varying assumptions for missing data from both treatment groups will be conducted. This sensitivity analysis will focus on missing data at the primary endpoint. Penalties for imputed missing values will be added for both treatment arms. The ANCOVA model for treatment regimen estimand will be conducted after penalties are added. The multiple imputation framework by Rubin (1987) will be used to summarize the results. The corresponding p-values of non-inferiority test will be shown by color scale in the figure.

Imputation under the noninferiority null hypothesis

After imputing the missing data used in the treatment-regimen estimand (Section 4.3.2), imputation under the noninferiority null hypothesis will be conducted by adding 0.4 (NIM) to the same imputed data of LY3209590 group only. The ANCOVA model for treatment regimen estimand will rerun using the adjusted data. The multiple imputation framework by Rubin (1987) will be used to summarize the results.

Including Inadvertently Enrolled Participants

The primary efficacy analysis will be repeated for the mITT population, including participants inadvertently enrolled, for both treatment regimen estimand and efficacy estimand.

Assuming unequal variances due to different group sizes

A sensitivity analysis will be performed on the treatment regimen estimand, using the same ANCOVA model described in Section 4.3.2 but assuming unequal variances to account for potential unequal residual variances due to different group sizes.

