## 9.3.2. Primary Endpoint/Estimand Analysis

The primary objective is to compare the HbA1c change from baseline to Week 26 between LY3209590 and insulin degludec and will be based on either of the 2 estimands: *treatment regimen estimand* for the US FDA submission and *efficacy estimand* for registrations in other countries.

The *treatment regimen estimand* will be estimated using the HbA1c data at baseline and Week 26 (Visit 22) for the EAS1, regardless of the use of study treatment or rescue medications. The missing measures at the primary endpoint will be imputed using multiple imputation by the retrieve dropout approach. The retrieved dropout participants are those who discontinue IP prior to Week 26 (Visit 22) but have non-missing measures at Week 26 (Visit 22). If there are only a limited number of retrieved participants that leads to a failure in performing the multiple imputation analysis, such as the model cannot converge, or the number of retrieved dropout participants is small, the missing HbA1c at Week 26 (Visit 22) will be imputed by return-to-baseline multiple imputations. After the imputation, the observed and imputed data will be analyzed by the analysis of covariance (ANCOVA). The model will include treatment, strata (country, and the type of basal insulin at randomization), and baseline value of the dependent variable. The statistical inference will be based on the multiple imputation framework by Rubin (1987).

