1.2. Study Design

- Study BDCU is a Phase 3, multicenter, randomized, open-label, comparator-controlled study to evaluate the efficacy and safety of once-weekly basal insulin (LY3209590) compared to insulin degludec in participants with T2D treated with basal insulin.
- The study includes a 3-week screening/lead-in period, a 78-week treatment period, and a 5-week safety follow-up period.
- Participants will continue prior stable diabetes therapy with 0 to 3 allowed non-insulin antihyperglycemic medications during the study.
- Participants will discontinue their previous basal insulin doses at randomization and will be assigned to either LY3209590 or insulin degludec U100.
- Assignment to treatment groups will be determined by an interactive web-response system (IWRS). Participants will be randomly assigned to 1 of the 2 treatment groups in 2:1 ratio (LY3209590 : insulin degludec) at Week 0 (Visit 3). Stratification will be by country, HbA1c stratum at Week -3 (Visit 1) (<8.0%, ≥8.0%), and the type of basal insulin regimen at randomization (a. typical once-daily basal insulin; b. U-300 or BID regimens).
- This is a treat-to-target study, both treatment groups will undergo titration to achieve an FBG target within the range of 80-120 mg/dL. The primary endpoint at Week 26 (Visit 22) is based on participants reaching stable insulin dose by 8 to 12 weeks and glycemic stability in advance of the 26-week primary endpoint Hemoglobin A1c measure.
- Rescue therapy will be considered during the treatment period if the participants meet the protocol criteria of severe, persistent hyperglycemia.
- If study intervention is permanently discontinued, the participant will be encouraged to continue participation in the study for continued monitoring. Both efficacy (including HbA1c) and safety data will continue to be collected per the schedule of activities in the protocol.

2. Statistical Hypotheses

Primary Hypothesis

The primary objective of this study is to test the hypothesis that LY3209590 is noninferior to insulin degludec on glycemic control as measured by change from baseline to Week 26 (Visit 22) in HbA1c in participants with T2D currently on basal insulin. Thus, the null hypothesis (H_{01}) to be tested is the difference in the change from baseline to Week 26 (Visit 22) in HbA1c (LY3209590 – insulin degludec) is greater than the noninferiority margin (NIM). The 2-sided 95% confidence interval (CI) will be used for testing the noninferiority.

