2.1. Multiplicity Adjustment

A graphical approach (Bretz et al. 2009; 2011) for multiple comparisons will be used to ensure the strong control of the overall type I error rate for testing the primary and key secondary (multiplicity adjusted) objectives. The overall significance level (α) will be set to 0.05. The total α will be used for the primary objective first, then the α will be allocated and transitioned to other key secondary objectives once the primary objective is met. Therefore, the noninferiority test for the primary objective will be based on the 2-sided 95% CI. Once the upper limit of the 2-sided 95% CI is below the NIM, the non-inferiority is achieved and the α of 0.05 will be distributed to test superiority for the key secondary objectives. If the p-value of the 2-sided test for one of the key secondary objectives is below the assigned α level, the superiority is demonstrated and the assigned α level will be distributed to the remaining objectives. The iterative test procedure continues until none of the remaining objectives can be demonstrated with their preserved α or all objectives are demonstrated successfully. The NIM of 0.4% (for treatment regimen estimand) and 0.3% (for efficacy estimand) will both be tested to meet different regulatory requirements. No multiplicity adjustments will be made for conducting separate analyses relative to the treatment regimen and efficacy estimands. Each estimand will have its own familywise error rate of 0.05.

For primary and key secondary efficacy objectives, the details of type I error control strategy are illustrated in the figure :

Both treatment regimen estimand and efficacy estimand will be used to assess these objectives. As they are intended for different purposes, no multiplicity adjustments will be made for conducting separate analyses relative to the treatment regimen estimand and efficacy estimands. In addition, no multiplicity adjustments will be made for evaluating other secondary and exploratory objectives, or for safety assessments.

3. Analysis Sets

The following analysis populations and data sets are defined for the purpose of analysis.

Analysis Populations/ Data Sets	Description			
Entered Population	All participants who sign the informed consent form			
Randomized Population	All randomized participants. Participants will be analyzed according to the			
	treatment they were assigned.			

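### The sensitivity analysis named for the noninferiority null does not guarantee that missing LY3209590 values are imputed at that null (minor; sensitivity analysis only)

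*SAP*

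**What the plan says.** For the treatment regimen estimand, Protocol Section 9.3.2 states: "The missing measures at the primary endpoint will be imputed using multiple imputation by the retrieve dropout approach". SAP Section 4.3.2 defines the donors as participants who stopped study treatment before Week 26 but have "measures at Week 26 in the same treatment" arm. The fallback applies when the model cannot converge or when at least one arm has "less than 8 participants who discontinued" treatment early and have an endpoint value. In that case, by Protocol Section 9.3.2, the missing values "will be imputed by return-to-baseline multiple imputations".

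On the margin, SAP Section 2.1 states: "The NIM of 0.4% (for treatment regimen estimand) and 0.3% (for efficacy estimand) will both be tested". SAP Section 2 sets the null as an LY3209590 minus degludec difference above the margin.

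SAP Section 4.3.3 then starts from the Section 4.3.2 imputations and specifies: "imputation under the noninferiority null hypothesis will be conducted by adding 0.4 (NIM) to the same imputed data of LY3209590 group only". The ANCOVA is rerun and the results are combined by Rubin's rules. Nothing in the section re-centres the LY3209590 values on the degludec arm before 0.4 is added. The same section also plans a two-way tipping point analysis with penalties in both arms, but gives no penalty grid.

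**The concern.** An imputation under the noninferiority null should place the missing LY3209590 outcomes at the degludec level plus the margin. The written step instead places them at the LY3209590 donors' own level plus the margin. The two agree only if the own-arm imputations show no difference between arms.

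If LY3209590 retrieved dropouts do better than degludec retrieved dropouts, by chance or in truth, that advantage is carried into the values meant to represent the null, and part of the penalty is lost. The result could then be reported as robust under the null when the missing values sat inside the margin. The same sentence also means different things depending on which imputation branch is triggered.

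**Working it through.** **Inputs from the documents.** Margin 0.4, SD 1.1, 626 and 313 randomized, 15% dropout at Week 26, and the threshold of 8 donors per arm.

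**Assumptions not in the documents.** The size of d, the number of donors, the missing fraction m in the LY3209590 arm, and unadjusted donor means in the standard error of d.

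**The plan's own figures.**
- Completers: 626 × 0.85 = 532 and 313 × 0.85 = 266.
- Trial SE = 1.1 × √(1/532 + 1/266) = 0.0826.
- Power at margin 0.4: Φ(0.4/0.0826 − 1.96) = 99.8% (stated: above 99%).
- Power at margin 0.3: Φ(0.3/0.0826 − 1.96) = 95.3% (stated: at least 95%).

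Both reproduce. The plan gives no figure for the sensitivity analysis itself.

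**Imputed gap.** After the step, the gap is d + 0.4. Its contribution to the overall difference is m × (d + 0.4). An imputation centred at the null contributes m × 0.4. The discrepancy is m × d.

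| d | imputed gap | contribution, m = 5% | contribution, m = 15% | discrepancy, m = 5% | discrepancy, m = 15% |
|---|---|---|---|---|---|
| −0.3 | 0.1 | 0.005 | 0.015 | −0.015 | −0.045 |
| 0 | 0.4 | 0.020 | 0.060 | 0 | 0 |
| +0.3 | 0.7 | 0.035 | 0.105 | +0.015 | +0.045 |

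**Simulation check.** Settings: 626:313, 15% missing, 5% retrieved dropouts, 20 imputations, ANCOVA with Rubin's rules, 150 replicates. With own-arm retrieved-dropout imputation the mean gap was 0.10, 0.40 and 0.73 at d = −0.3, 0 and +0.3. With return-to-baseline it was 0.40 at all three.

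**How large d can be by chance, with no true donor difference.**
- 16 and 8 donors: SE(d) = 1.1 × √(1/16 + 1/8) = 0.476. The gap falls below 0.2 with probability Φ(−0.2/0.476) = 34% and below 0 with probability Φ(−0.4/0.476) = 20%. By symmetry it exceeds 0.6 in 34% and 0.8 in 20%.
- 40 and 20 donors: SE(d) = 1.1 × √(1/40 + 1/20) = 0.301. The matching figures are 25% and 9% in each direction.

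**Effect on the estimate per SE of d.** Retrieved dropouts have a Week 26 value, so they are not missing. Taking the planned 15% as participants who stop treatment gives about 94 and 47.
- 16 and 8 retrieved: m = (94 − 16)/626 = 12.5%; shift = 0.125 × 0.476 = 0.06.
- 40 and 20 retrieved: m = (94 − 40)/626 = 8.6%; shift = 0.086 × 0.301 = 0.026.

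The range is about 0.03 to 0.06, against a trial SE of 0.083.

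**The case against.** The strongest reply is that the step does something coherent: it keeps the primary missing-data assumption and makes the missing LY3209590 outcomes worse by the full margin relative to it. Anchoring on degludec donors asks a different, reference-based question and uses the smaller arm's donors. The first part stands as a defence of the calculation, but not of its name, which refers to the null between the arms. The smaller-donor point is weak, because donor noise shared by both arms' imputations largely cancels in the treatment difference.

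A reader might infer that the analysis does not test the null it names, or that it is always lenient. The documents support neither. The ANCOVA result is still judged against the margin; only the centring of the missing values can drift. The drift goes either way, and where d is positive the written step is the stricter one.

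A reader might also infer that the tipping point analysis is no help. In fact the re-centred null is the point with an LY3209590 penalty of 0.4 − d and a degludec penalty of 0. It can be located once d is estimated from the imputed data. What remains is that the SAP plans no report of d and states no grid, so a reader of the results may not be able to find that point.

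The practical effect is also limited. With no true difference, the expected upper confidence limit is about 1.96 × 0.0826 = 0.16, or about 0.16 + 0.15 × 0.4 = 0.22 after the step. At 15% missing and |d| = 0.3, re-centring changes the conclusion only if the limit already lies within about 0.045 of 0.4. This stands, and it is why the point is minor.

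**Conclusion.** The point holds in limited form. On the retrieved-dropout path, Section 4.3.3 yields an imputed gap of d + 0.4 and does not guarantee the 0.4 that its title implies. The gap is right when d = 0 and, in expectation, under return-to-baseline. Otherwise the step is too lenient or too strict according to the sign of d.

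The sensitivity estimate is off by m × d: 0.015 to 0.045 for |d| = 0.3 with 5% to 15% missing, or about 0.03 to 0.06 per standard error of d in the two donor scenarios. These sizes rest on assumed values of d, donor counts and missing fraction. Fifteen percent is an upper working value for m, because participants who stop treatment but stay in the study are not missing.

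The primary test, alpha and sample size are unaffected, and nothing here shows that the noninferiority conclusion would change. Severity: minor.

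**What to change.** Change the step in SAP Section 4.3.3 as follows:
- Impute missing LY3209590 Week 26 values from the degludec retrieved-dropout model, given each participant's own baseline. Where the return-to-baseline fallback applies, use that instead.
- Add 0.4 to those values.
- Leave the degludec imputations as in Section 4.3.2, and rerun the ANCOVA with Rubin's rules.

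The expected imputed gap, given baseline, is then 0.4 whatever d is. The own-arm analysis can be kept alongside if it is labelled a one-arm delta penalty of 0.4; reporting d with it would let readers place it on the tipping point map.

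The cost is a short SAP edit and one changed imputation step. Relative to the current text the estimate moves by −m × d, so the sensitivity result may become more or less favourable to LY3209590 depending on the sign of d.

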4.3.4. Supplementary Analyses

Additional analysis may be conducted as needed.

4.4. Secondary Endpoints Analysis

4.4.1. Key Secondary Endpoints

A graphical approach (see Section 2.1) will be used to control the overall type I error for the primary objective and the key secondary objectives. The key secondary objectives will test the superiority of LY3209590 compared with insulin degludec for the following endpoints:

- 1) change from baseline in HbA1c at Week 26 (Visit 22);
- 2) the event rate of clinically significant nocturnal hypoglycemia (<54 mg/dL [3.0 mmol/L] or severe) during the treatment period up to Week 78 (Visit 37); and
- 3) time in glucose range between 70 and 180 mg/dL (3.9 and 10.0 mmol/L) inclusive collected during the CGM session prior to Week 26 (Visit 22).

4.4.1.1. **Definition of Endpoint(s)**

See Section 4.3.1 for the HbA1c change from baseline to Week 26 (Visit 22).

The hypoglycemia events will be based on participant entry into an e-diary which receives all blood glucose (BG) measurements performed by the participant and transmitted via Bluetooth from the study-provided glucometer. The nocturnal period is defined by midnight to 6 AM. The event rate of clinically significant nocturnal hypoglycemia (<54 mg/dL [3.0 mmol/L] or severe) will be based on the count of the hypoglycemia episodes in the nocturnal period and the corresponding exposure of study intervention.

The time in glucose range between 70 and 180 mg/dL (3.9 and 10.0 mmol/L) inclusive will be based on the percentage of CGM readings within the glucose range during the specific CGM session. The derivation of CGM parameters is provided in Appendix 6 (Section 6.6).

4.4.1.2. Main Analytical Approach

The superiority test in change from baseline to Week 26 (Visit 22) in HbA1c will be based on the same primary endpoint analysis described in Section 4.3.2.

The rate of participant-reported nocturnal hypoglycemia will be analyzed by a negative binomial regression. The analysis details are provided in Section 4.6.3.1.

The time in glucose range between 70 and 180 mg/dL (3.9 and 10.0 mmol/L) inclusive measured by CGM will be analyzed using an ANCOVA model for treatment regimen estimand and an MMRM model for efficacy estimand. The analyses are similar to the primary analysis described in Section 4.3.2 with additional term of baseline HbA1c stratum (<8.0%, $\geq8.0\%$) in analysis models. For treatment regimen estimand, For the treatment-regimen estimand, only participants with an observation either at baseline or at Week 26 (Visit 22) will be included in the analysis. The missing data at baseline will be imputed using multiple imputation with assumption of missing at random and at Week 26 (Visit 22) the missing data will be imputed by multiple imputation with the approach similar to the imputation used for the primary endpoint.

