4.4.2. Supportive Secondary Endpoints

4.4.2.1. Other Efficacy Endpoints

The analysis of continuous efficacy measures of change from baseline for:

- HbA1c at Weeks 52 and 78 (Visits 30 and 37),
- fasting glucose by SMBG at Weeks 26, 52 and 78 (Visits 22, 30 and 37), and
- CGM (selected) parameters at the 4-week sessions prior to Weeks 26, 52 and 78 (Visits 22, 30 and 37)

will be based on both treatment regimen estimand and efficacy estimand. Analysis of insulin dose will be based on efficacy estimand only.

For treatment regimen estimand, only participants with an observation either at baseline or at the endpoint visit will be included in the analysis. The missing baseline will be imputed using multiple imputation under assumption of missing at random. Missing data at the endpoint visit will be imputed using either retrieved dropout or return-to-baseline multiple imputation approach determined by the criterion described for the primary efficacy endpoint in Section 4.3.2. ANCOVA analysis will be conducted similar to that for the primary endpoint. An additional term of baseline HbA1c stratum (<8.0%, $\geq 8.0\%$) will be added into the model for the endpoints except analysis of HbA1c.

For efficacy estimand, participants with baseline and at least one post baseline observation will be included in the analysis. The longitudinal observations of actual and change from baseline in HbA1c up to Week 78 will be analyzed using the same MMRM model as for the efficacy estimand described in Section 4.3.2. The analyses of other continuous efficacy measures (insulin dose, fasting glucose and CGM parameters) will use an MMRM model similar to that for the primary endpoint with an additional term of baseline HbA1c stratum (<8.0%, $\geq 8.0\%$). A compound symmetry covariance structure will be used to model the within-participant errors for fasting glucose from SMBG and insulin dose.

Additional analysis are as specified below.

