4.9. Changes to Protocol-Planned Analyses

There are no changes to the analyses described in the protocol but additional details are provided.

5. Sample Size Determination

Approximately 939 participants will be randomly assigned to LY3209590 and insulin degludec in a 2:1 ratio. With the assumption of 15% dropout at Week 26 (Visit 22), approximately 532 and 266 participants will complete 26 weeks of treatment on LY3209590 and insulin degludec, respectively.

The primary objective of this study is to test the hypothesis that LY3209590 is noninferior to insulin degludec on glycemic control as measured by change from baseline to Week 26 (Visit 22) in HbA1c in participants with T2D currently on basal insulin.

Assuming a NIM of 0.4%, no true difference between treatment groups, and a SD of 1.1%, 798 completers (532 on LY3209590 and 266 on insulin degludec) will provide greater than 99% statistical power to show noninferiority between LY3209590 and insulin degludec using the upper limit of a 2-sided 95% confidence interval (LY3209590 – insulin degludec). This sample size also has at least 95% statistical power to show noninferiority between LY3209590 and insulin degludec) and insulin degludec using a 0.3% NIM at Week 26 (Visit 22).

The 798 completers will provide 95% statistical power to demonstrate the superiority (LY3209590 vs. insulin degludec) of change in HbA1c from baseline to 26 weeks (assuming a SD of 1.1% and true mean difference is -0.3%) using the alpha of 0.05.

The 798 completers will provide at least 95% statistical power to show the superiority of the percentage of time in glucose range between 70 and 180 mg/dL (3.9 and 10.0 mmol/L) inclusive during the CGM session prior to Week 26 (Visit 22) between LY3209590 and insulin degludec (assuming a SD of 18% and true mean difference is 5%) at alpha = 0.05.

The 798 participants will provide at least 80% statistical power to show the superiority of the event rate of clinically significant nocturnal hypoglycemia (<54 mg/dL [3.0 mmol/L] or severe) during treatment phase up to Week 78 (assuming event rate of 0.67 [SD = 2.6] and 1.1 [SD = 2.6] events per participant per year for LY3209590 and insulin degludec, respectively) using a negative binomial distribution at alpha = 0.05.

6. Supporting Documentation

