6.6. Appendix 6: Derivation of CGM Variables

Blinded CGM will be worn by participants at the following designated weeks:

- Two weeks in screening/lead-in period with the data download at Week 0 (Visit 3),
- Four weeks after the initiation of study treatment with the data download at Week 4 (Visit 7),
- Four weeks near the end of weekly titration period with the data download at Week 12 (Visit 15),
- Four weeks near the primary endpoint with the data download at Week 26 (Visit 22),
- Four weeks near the end of 1-year treatment with the data download at Week 52 (Visit 30),
- Four weeks near the end of study treatment period with the data download at Week 78 (Visit 37), and
- Four weeks after the end of study treatment period with the data download at Week 83 (Visit 802).

Linear interpolation will be used to impute the missing glucose readings during intervals >7 minutes and ≤ 15 minutes. Missing data will be imputed at a 5-minute interval using the BG value before and the one after the interval.

For example, the BG reading before the interval is 50 mg/dL at time 100 min, and the BG reading after interval is 70 at time 115 min, then the missing records will be imputed as:

- at time 105 min, BG reading=50+5*(70-50)/(115-100)=56.7, and
- at time 110 min, BG reading=50+10*(70-50)/(115-100)=63.3.

Glucose reading intervals >15 minutes will be treated as missing data and not be counted in the length of the analysis periods.

As shown in the table below, all the CGM derivations are based on the data from valid CGM periods of a day and period unless otherwise specified.

Period	Definition	Minimum Valid CGM Time Period for a Session		
Valid CGM Day	\geq 70% of expected values	\geq 3 valid CGM days within a visit defines a valid		
(00:00-23:59)	available (≥202 of 288 values)	CGM visit. A valid CGM session only includes valid		
		CGM visits.		
Valid CGM Nighttime	\geq 70% of expected values	\geq 3 valid CGM Nighttime periods within a visit		
(00:00-05:59)	available (≥50 of 72 values)	defines a valid CGM visit. A valid CGM session for		
		nighttime only includes valid CGM visits.		
Valid CGM Daytime	\geq 70% of expected values	\geq 3 valid CGM Daytime periods within a visit defines		
(06:00-23:59)	available 151 of 216 values)	a valid CGM visit. A valid CGM session for daytime		
		only includes valid CGM visits.		

Abbreviation: CGM = continuous glucose monitoring.

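### Time in range, efficacy estimand: participants with an observed Week 26 session but no valid baseline CGM session are excluded, whereas the treatment-regimen analysis imputes their baseline

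*SAP*

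**What the plan says.** **Treatment-regimen estimand.** SAP 4.4.1.2 sets an either/or entry rule for time in range: "For the treatment-regimen estimand, only participants with an observation either at baseline or at Week 26 (Visit 22) will be included in the analysis". It continues: "The missing data at baseline will be imputed using multiple imputation with assumption of missing at random". The baseline table in SAP 4.1 also specifies multiple imputation of baseline for CGM parameters under this estimand.

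**Efficacy estimand, time in range.** SAP 4.4.1.2 gives no entry rule of its own. It says "The analyses are similar to the primary analysis described in Section 4.3.2 with additional term of baseline HbA1c stratum". In 4.3.2 the efficacy-estimand population is "All participants in EAS2 with non-missing" "baseline measure and at least one non-missing" scheduled post-baseline value. The efficacy-estimand CGM row of the 4.1 table has no baseline imputation.

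**Efficacy estimand, other CGM parameters.** Here SAP 4.4.2.1 is explicit: "For efficacy estimand, participants with baseline and at least one post baseline observation will be included in the analysis".

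**Baseline CGM.** There is one lead-in session of about two weeks (SAP Appendix 6). A day is valid with at least 70% of expected readings, and at least 3 "valid CGM days within a visit defines a valid" CGM visit.

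**Rationale.** None is given for treating baseline differently under the two estimands. The Version 4 entry in the SAP history table records the baseline imputation as an addition and says no more.

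**The concern.** The key secondary endpoint is the level of time in range in the session before Week 26. A participant with a valid Week 26 session and no valid lead-in session therefore has a fully observed outcome. Only a pre-randomization covariate is missing. EAS2 does not exclude such a participant; the exclusion enters only through the model's population rule.

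The complete-baseline rule costs almost nothing for HbA1c, from which it is borrowed. Baseline HbA1c is the last non-missing value up to the first dosing day, and eligibility already requires a central-laboratory screening value. CGM has a single lead-in session. Protocol 5.1 asks for willingness to wear the device, not a valid session, and under Protocol 8.1.5.2 capture below 80% leads to re-education rather than screen failure. Some missing baselines can therefore occur.

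At stake are precision on an alpha-controlled endpoint in the analysis for countries outside the US, and the consistency of two analyses meant to address the same targeted population.

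**Working it through.** **Inputs from the documents.** SAP Section 5 and Protocol 9.5 give 798 completers (532:266, from 939 x 0.85) and power of at least 95%, "assuming a SD of 18% and true mean difference is 5%) at alpha = 0.05". Tests are two-sided (Protocol 9.3.1).

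**Inputs not in the documents (assumptions).** The share m of the 798 without valid baseline CGM is taken as 5%, 10% or 20%, equal in both arms. The baseline-to-Week 26 correlation rho is taken as 0.3 to 0.7. The documents do not say whether SD 18 is adjusted for baseline, so both readings are shown.

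**Step 1: the plan's own figure.** With 2:1 allocation, SE = SD x sqrt(4.5/N) and power = Phi(5/SE - 1.96). For N = 798, SE = 18 x sqrt(4.5/798) = 1.352 and power = Phi(3.699 - 1.96) = 95.9%. The stated figure reproduces.

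**Step 2: SD 18 read as baseline-adjusted.** Dropping a share m leaves N = 798(1 - m). A retained participant without baseline carries a fraction (1 - rho^2) of full information, so the effective N is 798 x [(1 - m) + m(1 - rho^2)].

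| m | N if dropped | SE multiplier | Power, dropped | Power, retained (rho 0.7 to 0.3) | Gain, points |
|---|---|---|---|---|---|
| 0% | 798 | 1.000 | 95.9% | - | - |
| 5% | 758 | 1.026 | 95.0% | 95.5-95.8% | 0.5-0.8 |
| 10% | 718 | 1.054 | 93.9% | 95.0-95.8% | 1.1-1.8 |
| 20% | 638 | 1.118 | 91.1% | 94.0-95.6% | 2.9-4.5 |

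Power drops below the stated 95% once m exceeds about 5.0%, and below 90% once m exceeds about 23%.

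**Step 3: SD 18 read as unadjusted.** If baseline explains 36% of variance (rho = 0.6), the residual SD is 18 x sqrt(0.64) = 14.4.
- 10% dropped: SE = 14.4 x sqrt(4.5/718) = 1.140, power 99.2%.
- 15% dropped (N = 678): SE = 14.4 x sqrt(4.5/678) = 1.173, power 98.9%.
- Retaining a 10% group: effective share 0.90 + 0.10 x 0.64 = 0.964, SE ratio sqrt(0.90/0.964) = 0.966. The interval is about 3.4% narrower.

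**Step 4: alpha.** The figure showing the alpha allocation is not reproduced in the text available. If time in range were tested at 0.025 rather than 0.05, power on the Step 2 reading would be 92.8% with none missing and 89.8% with 10% dropped.

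**The case against.** The strongest case against the point has five parts.

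- **The treatment-regimen analysis does not keep everyone without a baseline.** This stands. Without a baseline, a participant enters only with a Week 26 observation. Someone with only Week 4 or Week 12 data is in neither analysis. The two analyses differ over participants with a Week 26 session, and for Week 26 itself over those with no earlier intercurrent event.
- **Missing baseline may be rare.** A reader might infer that baseline CGM is easily lost. The documents do not show that: three valid days is a low bar for an 11-17 day lead-in, sites upload each session, and the vendor flags low capture. They do not show the opposite either, because no rate is given.
- **The power loss depends on assumptions.** This stands. It rests on the assumed rate and on how SD 18 is read. The 798 is also only an approximation to the MMRM's information, since that model uses sessions at Weeks 4, 12, 26, 52 and 78 and takes some information from participants who stop early.
- **Different data sets for different estimands are legitimate, and a complete-baseline MMRM is ordinary practice.** Both are true. But EAS1 and EAS2 differ because of intercurrent events, and a missing lead-in session is not one.
- **The SAP partly covers this.** Appendix 6 plans a sensitivity analysis using all available CGM data, and 4.4.2.1.1 plans summaries of missing-data patterns. The sensitivity analysis covers unnamed selected parameters and cannot help a participant with no lead-in data. The summaries will show the size of the problem but will not change the analysis.

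**Conclusion.** The asymmetry is in the SAP. It is explicit for the other CGM parameters and follows from the cross-reference to 4.3.2 for time in range. Participants with an observed Week 26 value are discarded from the efficacy-estimand analysis for want of a covariate that the SAP already imputes for the other estimand, and no reason is stated.

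The consequence is a modest loss of efficiency and consistency. On the adjusted reading of SD 18, the margin above the stated 95% is used up at about 5% missing. On the unadjusted reading with 36% of variance explained, power is hardly affected and the gain is a slightly narrower interval.

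A reader might go further and infer that the comparison is biased or that the endpoint is underpowered. The documents support neither. Baseline CGM precedes the first dose, so the exclusion does not depend on treatment received. An underpowered endpoint would need both a missing-baseline rate that the documents do not give and the less favourable reading of the SD.

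**What to change.** In SAP 4.4.1.2, 4.4.2.1 and the baseline table in 4.1, write out the efficacy-estimand entry rule for CGM measures: all EAS2 participants with at least one post-baseline session. Then specify one of two ways to handle a missing baseline:

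1. the multiple imputation under missing at random already specified for the treatment-regimen estimand; or
2. overall-mean imputation of baseline, ignoring arm, with a missing-baseline indicator in the model. This needs the observed CGM value as the response, because change from baseline is undefined for these participants.

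If the sponsor prefers to keep the complete-baseline rule, 4.4.1.2 should say so directly and justify the difference between estimands.

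The cost is a few sentences of SAP text and minor programming. Option 1 adds slight complexity in combining multiple imputation with the MMRM; option 2 does not. Data collection, the estimands and the alpha allocation are unchanged.
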